**Table 4: Ibrutinib Dose Reduction**

Dose Reduction	Ibrutinib Dose
1	420 mg
2	280 mg

Please see Section 4.2.1 for guidelines for management of ibrutinib in participants who require treatment with a strong CYP3A inhibitor.

### 3.3.4 Dose Modifications for Lenalidomide

Sample guidelines for dose delay and modification of lenalidomide are shown in **Table 5** and **Table 6** for the dose levels for lenalidomide dose reduction.

**Table 5: Guidelines for Dose Delay or Modification of Lenalidomide**

Event(s)	Dose Delay or Modification during a cycle
Neutropenia: • Grade 3 (ANC <1,000/ $\mu$ L) for $\geq$ 7 days, OR • Grade 4 (ANC <500/ $\mu$ L) for any duration	

Hold lenalidomide.

Administer growth factors (e.g., G-CSF for neutropenia as indicated).

-If ANC < 1000/<math>\mu</math>L for <math>\leq</math> 7 days, administer full dose of study treatment for the next cycle.

-If ANC < 1000/<math>\mu</math>L for <math>></math> 7 days, reduce the dose of lenalidomide by 1 dose level.

For subsequent episodes, dose reduction 2 of lenalidomide and drug discontinuation will be considered.

If the primary cause of neutropenia is thought to be lymphoma infiltration into the bone marrow, the Principal investigator may elect not to reduce the dose of lenalidomide .

Febrile neutropenia or neutropenia with infection	

Hold lenalidomide until resolution.

Thrombocytopenia: • Grade 3 (decrease to <50,000/ $\mu$ L) associated with > Grade 2 bleeding, OR • Grade 4 (decrease to <25,000/ $\mu$ L) with or without bleeding	

Hold lenalidomide.

-If platelet count < 50,000/<math>\mu</math>L for <math>\leq</math> 7 days, administer full dose of study treatment for the next cycle.

-If platelet count < 50,000/<math>\mu</math>L for <math>></math> 7 days, reduce the dose of lenalidomide by 1 dose level.

For subsequent episodes, dose reduction 2 of lenalidomide and drug discontinuation will be considered.

Grade 1 or 2 neutropenia and/or thrombocytopenia	

No dose reduction or delay.

Rash: • Any Grade desquamating (blistering), OR • Grade 4 non-blistering	

Discontinue lenalidomide.

Thromboembolic event $\geq$ Grade 3	

Hold lenalidomide.

Initiate therapeutic anticoagulation as clinically indicated, please evaluate interactions with other study drugs.

Resume lenalidomide without dose modifications at Day 1 of next cycle if benefit of therapy outweighs bleeding risk.

Hyperthyroidism or hypothyroidism $\geq$ Grade 2	

Hold lenalidomide.

Evaluate etiology & initiate appropriate therapy.

Reduce lenalidomide by 1 dose level at Day 1 next cycle. Start new cycle when participant meets cycle initiation criteria.

Event(s)	Dose Delay or Modification during a cycle
Creatinine Clearance <60 mL/min (CrCl, Cockcroft-Gault)	

-CrCl 30–60 mL/min: 10 mg every 24 hours

-CrCl <30 mL/min: hold lenalidomide

• If CrCl becomes >60mL/min for a minimum of 2 cycles, may escalate to the prior dose at investigator's discretion.

Any other Grade 4 toxicity or unmanageable Grade 3 toxicity attributed to lenalidomide	

• Hold lenalidomide.

-If improves to <math>\leq</math> Grade 2 in <math>\leq</math> 7 days, administer full dose of study treatment for the next cycle.

-If improves to <math>\leq</math> Grade 2 in <math>></math> 7 days, reduce the dose of lenalidomide by 1 dose level.

• For subsequent episodes, dose reduction 2 of lenalidomide and drug discontinuation will be considered.

**Table 6: Lenalidomide Dose Levels Reduction**

Dose Levels	Lenalidomide Dose
Dose level 1	15 mg
Dose level -1	10 mg
Dose level -2	5 mg

### 3.4 ON STUDY ASSESSMENTS/EVALUATIONS

The following describes all tests and procedures to be conducted on the study and during treatment. Assessments will be performed according to the Study Calendar, [Appendix D](#).

#### 3.4.1 Timing of Visits

For each time period, consider the following order of assessments:

- **Screening:** Refer to section [2.2](#)
- **Baseline:** Baseline assessments should be performed within 14 days of initiating study treatment unless otherwise specified on the Study Calendar. Tests performed as part of screening do not need to be repeated if they were performed within the specified window prior to initiating treatment.
- **Study Drug Administration:** See Section [3.2](#). Treatment will be given for a maximum of 6 cycles of induction therapy, until unacceptable toxicity or until any other criteria is met per Section [3.8.1](#). Dose delay of up to 6 weeks from the planned start of an induction cycle is permitted to allow for recovery from toxicities. A delay of more than 6 weeks will require the participant to be taken off treatment.
- **Pre-Cycle 1 (C1D1) of Induction Therapy:** Laboratory tests are required to be collected pre-dose of Day 1 of Cycle 1 (within 24 hours).

- **Pre-Subsequent Cycles (D1 C2-C6) of Induction Therapy:** After Cycle 1, pre-dose assessments may be performed up to 3 days prior to Day 1 of a cycle except where otherwise noted.

**Response Assessments:** Response assessments will be done per Section [3.4.3.1](#) below. Once treatment is complete, participants will be restaged per Section [3.5](#).

- **Unscheduled Visits:** In the event of an unscheduled/unplanned visit (e.g., additional clinical assessment(s) due to toxicity), the investigator should use best clinical judgement as to the necessary assessments. In the event that the decision is made to continue treatment, all tests/assessments as required by the next visit on the Study Calendar ([Appendix D](#)) should still be conducted (or repeated) within the applicable windows. If a decision is made to discontinue treatment, the participant should have an End of Treatment Visit followed by post-therapy follow-up with tests/assessments completed (or repeated) within the applicable windows.

- **Post Treatment Evaluations:** See Section [3.5](#)

### 3.4.2 Description of Procedures

- Medical history: a review of treatment history, any ongoing medical conditions and medical history pertaining to eligibility on study and involvement during study.
- Physical exam: review of organ systems, weight, and vital signs (i.e., temperature, pulse, respirations, blood pressure).
- Performance status (ECOG): an assessment of activities of daily living; see [Appendix A](#)
- Ophthalmologic evaluation and VTE risk assessment at baseline and during treatment as clinically indicated
- Laboratory assessments: the following comprises the required tests/analytes per panel. These may be performed at CLIA (or equivalent) certified laboratories outside NIH and results forwarded to the study team for review and management. Given that the methodologies utilized are similar across all laboratories, no significant variability is expected and there is no anticipation that study data will be affected.
  - CBC with differential: includes Neutrophils, Lymphocytes, Monocytes, Eosinophils, Basophils, WBC, RBC, Hemoglobin, Hematocrit, RBC Indices, MCV, RDW, and Platelets.
  - Panels:
    - Acute care panel: includes Sodium (NA), Potassium (K), Chloride (CL) Total CO2 (Bicarbonate), Creatinine, Glucose, Urea nitrogen, and eGFR.
    - Hepatic panel: includes Alkaline Phosphatase, ALT/GPT, AST/GOT, Total Bilirubin, and Direct Bilirubin.
    - Mineral panel: includes Albumin, Calcium, Magnesium, and Phosphorus.
  - Other: LDH, Uric Acid
  - TSH and T3 and/or T4 if needed
  - PT/ PTT
  - Lymphocyte phenotyping TBNK

- HIV 1/2 antibody, Hepatitis B surface antigen (HBsAg), Hepatitis B surface antibody (HBsAb), Hepatitis B core antibody (HBcAb), and Hepatitis C antibody (HCV Ab) to determine eligibility
- HBV and HCV viral load in positive participants to determine eligibility and to monitor for reactivation (see Section [4.1.2](#))
- CMV and EBV PCR
- Pregnancy test: Urine or serum HCG with a minimum sensitivity of 25 mIU/mL for individuals of child-bearing potential:
  - Individuals of childbearing potential (IOCBP) with regular or no menstruation must have a pregnancy test weekly for the first 21 days and then every 21 days while on lenalidomide therapy (including breaks in therapy); at discontinuation of lenalidomide and at 30 Day safety visit.
  - A FCBP with irregular menstruation must have a pregnancy test weekly for the first 21 days and then every 14 days while on lenalidomide therapy (including breaks in therapy), at discontinuation of lenalidomide and at Day 14 (+/-1 day) and at 30 Day safety visit.
- 24-hour urine creatinine clearance (if needed to measure CrCl in cases where serum creatinine >1.5 mg/dl)
- Urinalysis
- Quantitative Immunoglobulin Panel
- EKG to determine eligibility
- Imaging evaluations:
  - CT scans (chest, abdomen, and pelvis); may be adjusted to assess additional known sites of disease
  - Brain MRI
  - F-FDG-PET Scan brain and body (must be performed at NIH only). Additional PET/MRI may be performed as clinically indicated.

These scans (with the exception of F-FDG-PET) may be performed outside of the NIH and the result forwarded to the study team for review at screening or any time during the study. Given that the methodologies utilized are similar across all facilities, no significant variability is expected and there is no anticipation that study data will be affected.

- Lumbar puncture/Ommaya tap for CSF studies including protein, glucose, cell count/differential, cytology, and flow cytometry to determine eligibility and during the study if clinically indicated.
- Bone marrow aspiration/biopsy should be performed within 3 months prior to starting protocol treatment. May be repeated after Cycle 6 if the previous test result was positive or if otherwise clinically indicated.
- Study drug administration schedule- see Section [3.2](#)
- Adverse events and concomitant medication review: Adverse events and concomitant medication will be continuously monitored throughout the study until disease progression

or end of treatment visit. Adverse events that occur beyond 30 days after the last administration will be recorded per [6.1](#).

- Correlative studies: Refer to section [5](#)

### 3.4.3 Additional Information

#### 3.4.3.1 Response Assessments

Participants will be restaged at the following time points. Response assessments will be done by investigators. For additional details on response criteria, see Section [6.3](#).

- After cycle 1 (within 7 days prior to treatment on day 1 of cycle 2)
- After cycle 3 (within 7 days prior to treatment on day 1 of cycle 4)
- After cycle 6 (cycle 6 day 21 +/- 7 days)

**NOTE:** If a participant stops treatment for any reason other than disease progression before completion of 6 cycles, response assessments should continue as listed in Study Calendar ([Appendix D](#)).

**NOTE:** Restaging scans should only be performed based on involved sites of disease at baseline (e.g., patients with CNS disease only should undergo restaging MRI brain and PET brain while those with systemic disease should also undergo CT C/A/P and PET torso).

#### 3.4.3.2 Disease Progression

At the time of suspected or confirmed disease progression, the following are required:

- Imaging by MRI brain, CT scan, and FDG-PET (only if can be performed at NIH)
- Lumbar puncture/Ommaya tap for CSF studies including protein, glucose, cell count/differential, cytology, and flow cytometry
- Ophthalmologic evaluation (only if ocular involvement was noted at baseline evaluation)
- Symptom-guided clinical assessment with physical exam
- Lymphocyte phenotyping TBNK

**NOTE:** In the event that disease progression is not confirmed, yet a decision is made to initiate a new anti-cancer treatment for any reason, all of these assessments should be done prior to start of the new therapy.

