### 3.5.4 Follow-Up Visits – Survival/Post-Disease Progression

Once participants progress or start use of alternative antineoplastic therapy, they will be contacted, approximately every 3 months (+/- 14 days), for a maximum of 10 years to assess survival and the use of alternative antineoplastic therapy and stem cell transplant until withdrawal/end of the study (Section [3.8.2](#)).

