### 6.3.1 Response Criteria for PCNSL

The following response criteria as per the CNS lymphoma working group ([\[35\]](#)) will be used for participants on study with PCNSL:

Response	Brain Imaging	Corticosteroid dose	Eye examination	CSF cytology
CR	No contrast enhancement	None	Normal	Negative
CRu	No contrast enhancement	Any	Normal	Negative
	Minimal abnormality	Any	Minor RPE abnormality	Negative
PR	50% decrease in enhancing tumor	Irrelevant	Minor RPE abnormality or normal	Negative
	No contrast enhancement	Irrelevant	Decrease in vitreous cells or retinal infiltrate	Persistent or suspicious
PD	25% increase in lesion	Irrelevant	Recurrent or new ocular disease	Recurrent or positive
	Any new site of disease: CNS or systemic			

Abbreviations: CR, complete response; CRu, unconfirmed complete response; RPE, retinal pigment epithelium; PR, partial response; PD, progressive disease

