#### 6.3.5 Progressive Disease (PD) or Relapsed Disease

Progressive disease or relapsed disease (after CR) is defined as:

1. Appearance of any new nodal lesion  $\geq 1.6$  cm in greatest tumor dimension or  $\geq 1.1$  cm in short axis during or after the end of therapy, even if other lesions are decreasing in size.
2. Appearance of any new unequivocal extra-nodal lesion measuring  $>1.0$  cm, not thought to be benign by the reviewer, even if other lesions are decreasing in size
3. At least a 50% increase from the nadir in the sum of the product of diameters of any previously involved nodes, or in a single involved node, or in the size of other lesions (e.g., splenic or hepatic nodules). To be considered PD, a lymph node with a diameter of the short axis of  $<1.0$  cm must increase by  $\geq 50\%$  and to a size of  $1.5 \times 1.5$  cm or more than 1.5 cm in the long axis.
4. At least a 50% increase from the nadir in the longest diameter of any single previously identified node more than 1 cm in its short axis.
5. Cytology confirmation of DLBCL is required when there is an appearance on CT of a new lesion  $\geq 1.5$  cm in its long axis and is PET-negative.

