#### 17.4.2 End of Treatment and Post-Treatment Follow-Up

Studies	End of Treatment  Within 30 days after treatment discontinuation	Disease Progression (PD) 	Safety Post-Treatment Follow-Up		Prior to Disease Progression  Q 3 months for Year 1, Q 4 months for Year 2, Q 6 months for Year 3, Q 12 months for Years 4-10	Post-Disease Progression Survival Every 3 months for up to 10 years
			Day 14	Day 30		
Scheduling Window:	±7 days	ASAP	±1 days	+7 days	±14 days for Q 3, 4 months, ±21 days for Q 6 months, ±28 days for Q 12 months	±14 days
Interim History	X			X	X	
Physical and ECOG PS	X	X		X	X	
Vital Signs and Weight	X			X	X	
CBC/diff, platelets	X			X	X	
Acute Care Panel, Mineral Panel, Hepatic Panel	X			X	X	
LDH	X			X	X	
Uric Acid	X			X	X	
Serum or urine HCG (for IOCBP) 	X		X	X		
HBV DNA 	X			X	X	X
TBNK and Quant. IG Panel	X				X	
MRI brain		X			X	
CT scans (C/A/P) 		X			X	
 F-FDG-PET Scan brain and body		X				
Lumbar puncture/Ommaya tap with CSF Testing to include glucose, protein, cell count/differential, cytology, and flow cytometry		X				
Bone marrow biopsy and aspirate		X				

Studies	End of Treatment  Within 30 days after treatment discontinuation	Disease Progression (PD)  ASAP	Safety Post-Treatment Follow-Up		Prior to Disease Progression  Q 3 months for Year 1, Q 4 months for Year 2, Q 6 months for Year 3, Q 12 months for Years 4-10	Post-Disease Progression Survival Every 3 months for up to 10 years
			Day 14	Day 30		
Scheduling Window:	±7 days		±1 days	+7 days	±14 days for Q 3, 4 months, ±21 days for Q 6 months, ±28 days for Q 12 months	±14 days
Ophthalmologic Evaluation		X				
Symptoms/Adverse Events Assessment 	X	X		X		
Concomitant Medication Review	X			X		
Research bloods, saliva/buccal (baseline only), CSF samples (if Ommaya) See Section 5.1.	X	X			X	
Research Tissues (archival/fresh biopsy) 		X				
Survival Status						X

 To be done within 30 days (±7 days) after treatment discontinuation (i.e., may coincide with the safety follow-up visit). If treatment is discontinued for a reason other than disease progression, assessments should be repeated at the time of progression. If a subject initiates new anti-cancer therapy, assessments should occur before the first dose of the new anti-cancer therapy.

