 To be done as soon as possible after disease progression is identified. If a subject initiates new anti-cancer therapy, assessments should occur before the first dose of the new anti-cancer therapy.

 All post-treatment visit(s) may be completed by remote visit with a member of the study team (e.g., if the subject is not able to return to the NIH CC). Required labs/scans can be obtained by a local provider, with results sent in. A subject may be referred to their local provider or asked to come to the NIH CC for an in-person assessment, if clinically indicated, and at the discretion of the investigator. Prior to disease progression, follow-up to occur every 3 months for year 1 (±14 days), every 4 months for year 2 (±14 days), every 6 months for year 3 (±21 days), and then yearly (±28 days) for years 4-10 or until disease progression. After disease progression or starting a new anti-cancer therapy, survival follow-up contact visits should occur every 3 months for a maximum of 10 years post-treatment.

 Urine and/or serum HCG in participants of childbearing potential. See additional pregnancy testing requirements in Section 3.4.2

 Participants on HBV prophylaxis will have HBV DNA levels obtained for 12 months after the last cycle of therapy per Section 4.1.2.

 CT scans (C/A/P) are to be performed in restaging only if systemic disease present on baseline CT and/or PET imaging.

 Adverse event evaluation begins immediately after the first dose of study drug and continues throughout the treatment/follow-up portion of the study.

 Archival and/or Fresh Tissue Biopsy for gene expression profiling, mutational analysis, and DNA/RNA sequencing are optional at both baseline and at disease progression.

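### At suspected progression, Section 3.4.3.2 requires an eye examination only if the eye was involved at baseline, although new ocular disease counts as progression in PCNSL

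*Combined protocol and SAP*

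**What the plan says.** Section 3.4.3.2 opens its list with "At the time of suspected or confirmed disease progression, the following are required". Brain MRI, CT and CSF studies carry no condition. PET is required only where it can be done at NIH. The eye examination is the one item tied to baseline disease: "Ophthalmologic evaluation (only if ocular involvement was noted at baseline evaluation". A symptom-guided clinical assessment with physical examination is required of everyone. A note applies the same list before any new anti-cancer treatment when progression has not been confirmed.

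The PCNSL table in Section 6.3.1 includes in its progression row "Recurrent or new ocular disease" and, separately, "Any new site of disease: CNS or systemic".

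In Appendix D, Section 17.4.2, the disease-progression column marks "Ophthalmologic Evaluation" with no footnote or condition on that row. Footnote 2 gives the timing of the column: "To be done as soon as possible after disease progression is identified".

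Section 3.5.4 describes what follows: "Once participants progress or start use of alternative antineoplastic therapy, they will be contacted". That contact covers survival, later therapy and transplant, not disease status.

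**The concern.** New ocular disease can only occur in a participant whose eye was not involved before. That is the group whom Section 3.4.3.2 excuses from the examination. The progression definition and the assessments meant to establish progression therefore do not match for this one component.

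At stake are the secondary time-to-event endpoints. Under Section 10.4.3, PFS counts progression or death as events. Under Section 6.3.8, DOR ends when recurrence or progression is objectively documented. An ocular relapse that is not looked for is recorded late or never, and both errors lengthen PFS and DOR. Section 1.2.1 names the eye among the sites where this disease arises.

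**Working it through.** The plan gives no figure on this point, so the check is a comparison of its sections.

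**1. Rules for the eye, in time order, for a participant with a clear eye at baseline**

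| Stage | Source | Eye examination required? |
|---|---|---|
| On treatment, after cycles 3 and/or 6 | 17.4.1, footnote 9 | No; only if positive at baseline |
| On treatment, other | 3.4.2 | Only as clinically indicated |
| Follow-up before progression | 17.4.2 | None listed |
| Suspected or confirmed progression | 3.4.3.2 | No; only if involved at baseline |
| Before new therapy, progression unconfirmed | 3.4.3.2, note | No; same list |
| Progression identified | 17.4.2, progression column | Yes, unconditional |

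The only scheduled examination after baseline is the last row, and Section 3.4.3.2 withholds it.

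**2. Does the calendar settle the matter?** Section 3.4 says that assessments follow the calendar. The progression column, however, applies once progression has been identified. It does not cover suspected progression, where the examination would be what establishes the event.

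**3. Is the missing condition in the calendar just shorthand?** The calendar states baseline conditions elsewhere: in 17.4.1, footnotes 5 to 9 for CT, body PET, CSF, marrow and eye; in 17.4.2, footnote 6 for CT. The eye row in 17.4.2 has none.

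**4. Which participants?** The explicit ocular criterion is in the PCNSL table. The SCNSL progression criteria in Section 6.3.5 have no eye item, and a new extranodal lesion must exceed 1.0 cm. The point is therefore made for PCNSL.

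**5. Which relapses?** If MRI, CSF or CT also shows progression, the event is scored. If nothing raises suspicion, Section 3.4.3.2 is never triggered. What remains is suspected progression with the other tests negative, disease confined to the eye, and no eye examination prompted by the symptom-guided assessment. If new therapy then starts, Section 3.5.4 contact would not record the ocular event. PFS would run on to death or censoring.

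**6. Which endpoints?** PFS and DOR. The primary endpoint (Section 10.4.2) is defined by completing at least 2 cycles without stopping for toxicity, and OS by death. Neither uses progression as an event.

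**7. Size.** The documents give neither the number of expected progressions nor the share that begin in a previously clear eye, so no expected count or probability follows. All that can be shown is what one event would weigh. Take the 10 evaluable participants of Section 10.2 with no censoring. The fall in the Kaplan-Meier curve at one event is the current estimate divided by the number at risk:

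- first event: 1.0 × 1/10 = 0.10
- with 5 still at risk: 0.5 × 1/5 = 0.10

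One event never scored thus leaves the curve 10 points too high just after its true date, whether early or late. An event scored late only moves the step to the right.

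**The case against.** The strongest reply is that the route to a missed event is narrow. Eye symptoms should lead, through the symptom-guided assessment that Section 3.4.3.2 requires of everyone, to an eye examination. Section 3.5 also allows referral or an in-person visit when clinically indicated. The list is a minimum and forbids nothing. This stands as a limit on the size of the problem. It does not remove the mismatch, because neither provision requires an eye examination, and the wording in Section 3.4.2 on clinical indication covers only baseline and treatment.

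A second reply is that text and calendar may be complementary. The progression column also marks PET without the NIH-only condition that Section 3.4.3.2 states, so the calendar sometimes leaves conditions to the text. Baseline-guided testing is also a stated principle for restaging scans. This stands in part: which reading governs is unclear. Under the reading in which the text governs, new ocular disease is a progression criterion with no required test.

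A reader might infer more than the documents support:

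- **Silent eye relapse in follow-up.** No eye examination is scheduled there, but a relapse that raises no suspicion does not trigger Section 3.4.3.2. Changing that section would not find it.
- **A stated probability of an affected event.** This needs an assumed ocular share and an assumed number of progressions, and the documents give neither. It would also count relapses that other tests or symptoms would reveal.
- **A missed event that weighs more later on the curve.** Without earlier censoring it does not, as shown above.

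**Conclusion.** The mismatch is real and the point holds in a limited form. In a PCNSL participant whose eye was clear at baseline, a first relapse confined to the eye could be missed or dated late under Section 3.4.3.2 as written. The bias would run towards longer PFS and DOR and is expected to be slight, because the affected situation is narrow. Its size cannot be computed from the documents.

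The conclusion assumes that sites follow the text of Section 3.4.3.2 rather than the calendar, and that the symptom-guided assessment does not always lead to an eye examination. This is a low-priority correction that is worth making because it is cheap.

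**What to change.** Reconcile Sections 3.4.3.2, 6.3.1 and 17.4.2. Remove the baseline-involvement condition from the eye item in 3.4.3.2, at least for participants scored by 6.3.1 (PCNSL), so that the assessments at suspected progression cover every component of the progression definition. The note on new therapy before confirmed progression then follows without further change. Add a sentence that ocular progression is dated at that examination. If the change is limited to PCNSL, say so in both the text and the calendar, because the calendar row does not separate PCNSL from SCNSL.

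The cost is a one-line edit plus the dating sentence, and one eye examination per affected participant at suspected progression. The calendar already lists that examination once progression is identified. Sample size and the primary analysis do not change.
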